9.7.3 Yearly analyses

An analysis on the cumulative enrolled patients will be performed on a yearly basis along with a short statistical report at the time of Periodic Safety Update Report/Periodic Benefit-Risk Evaluation Report (Periodic Safety Update Reports//Periodic Benefit Risk Evaluation Report) updates.

9.7.4 Handling of Missing Data

Full details on handling of all missing data, which are common in observational studies, will be described separately in the SAP. The SAP will describe the methods for identifying where missing data methods should be applied, the techniques for identifying the type of missing information and the appropriate imputation methods to be used, if any, as per European Medicines Agency (EMA) 2010 guidance on missing data (6).

The proportion of missing data will be reported for each measured variable in the study.

9.8 QUALITY CONTROL

9.8.1 Data collection, validation and data quality control at MAH/MAH representative level

A study manual, including for-cause monitoring, as appropriate for the study design, will be developed and implemented.

Data will be collected using e-CRF.

The computerized handling of the data by the MAH/MAH representative after receipt of the data through e-CRFs may generate additional requests to which the participating Investigator is obliged to respond by confirming or modifying the data questioned. The requests with their responses will be appended to the e-CRFs held by the Investigator and the MAH/MAH representative.

Data collection and validation procedures will be detailed in appropriate operational documents.

9.8.2 Data quality control at site level

Data quality control will be performed on active sites at site level (i.e., those that have enrolled at least one patient).

Quality Control will be performed by qualified designated personnel in each country.

The methodology of data Quality Control and appropriate consecutive corrective actions will be detailed in the study manual.

During the site initiation visit, the monitor will provide training on the conduct of the study to the investigator, co-investigator(s), and all site staff involved in the study. In order to ensure the integrity of the data, sites will be monitored. Site monitoring will be performed by IQVIA clinical research associates to examine compliance with the protocol and adherence to the enrolment process, data collection procedures, to assess the accuracy and completeness of submitted clinical data, and to verify that records and documents are being properly maintained for the duration of the study. The monitor will perform source data verification by review of original subject records. The monitor will also validate expedited reporting of AE/SAE per local regulations.

The monitor will close out each site after the last subject's final follow-up assessment is completed, all data have been entered and all outstanding monitoring issues have been resolved or addressed. All monitoring procedures and frequency of monitoring visits will be described in a study manual. Monitor contact details for each participating site will be maintained in the Investigator Site File.

Representatives of the MAH quality assurance unit/monitoring team and competent regulatory authorities must be permitted to inspect all study-related documents and other materials at the site,

including the Investigator Site File, the completed e-CRFs and the subjects' original medical records. Audits may be conducted at any time during or after the study to ensure the validity and integrity of the study data.

In addition, high data quality standards will be maintained and processes via data management procedures, as previously described in Section 9.6.

9.9 LIMITATIONS OF THE RESEARCH METHODS

Potential limitations of the study design and measures proposed to address them include the following:

Enrollment bias: Sites will be expected to consecutively enroll eligible subjects and to maintain tracking logs of all subjects meeting eligibility criteria, along with reasons for non-enrolment.

Healthy user bias/depletion of susceptibles: Long term users of Insuman + the pump (i.e. from the clinical trials) have generally shown tolerance to the treatment and may be at lower risk of some of the identified risks and other AEs than new users. This bias can be addressed by analyzing data separately for long term users and new users.

Inconsistent interpretation of e-CRFs by participating centers: All centers/sites will undergo standardized training and utilize standardized documentation for completing of CRFs at enrollment and for each follow-up assessment.

Follow-up bias: A low lost to follow-up rate of approximately 5% is expected, in part due to the ability of this observational study to follow up directly with subjects even if they do not return to the enrolling center. A very low rate will be envisioned as the patient will have to refill regularly the pump and therefore to come back to enrolling center. Maintaining a low rate of lost to follow-up will lower the risk of bias that could result, for example, if subjects with AEs were less likely to return to the study investigator for follow up.

Due to the Minimed Implantable pump phase out, the initial targeted recruitment (ie, initially 400 patients and up to 50 new patients per year) will not be achieved. The potential impact on the statistical analyses performed will be described in the amended SAP.

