All AEs will be followed until resolution or until the end of the follow-up period, whichever comes first.

Data Sources

Investigators at each site will collect and provide pre-specified data on study participants at baseline and during follow-up visits. Data elements provided by investigators and staff will be collected from information routinely recorded in the medical record, or will be prospectively recorded for the purposes of the study. No visits or examinations, laboratory tests or procedures are mandated as part of this study.

Information required to validate Serious Adverse Events (SAEs) will be requested from investigators and medical facilities as needed by the medical monitors, which may include confirmation of diagnoses or conditions and relatedness of AEs by the treating investigators, medical records including laboratory test results and imaging procedure results, and death certificates.

Study Size

This is a descriptive study that is not testing a hypothesis. As such, a formal sample size calculation is not performed. It is planned to recruit all patients who are willing to participate, from all trained investigators in certified centers in all participating European countries, and without a minimum designated for any country or region. The projected study size will be approximately 260 patients. No new patient or a very limited number of newly implanted patients is expected.

Data Analysis

Eligible patients will be those who have signed an informed consent form (ICF) and have received at least one dose of Insuman Implantable 400 IU/mL

• Primary analysis

Since the primary objective is to monitor the important identified risks, the analysis will be descriptive and the multiplicity control will not be considered.

For the important identified risks including severe hypoglycaemia, hyperglycaemia due to underdelivery of insulin, pump pocket infections, skin erosion, and abnormal healing, the time to first event will be depicted by the Kaplan-Meier plot. The cumulative event rate and its 95% confidence interval (CI) will be presented yearly.

The cumulative risk over the entire study and the instantaneous risk expressed as the hazard function over time will be presented graphically according to the time expressed in years and using a kernel smoothing method. A horizontal line will represent the incidence rate calculated, as number of patients with one or more events divided by the number of patients treated.

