9 RESEARCH METHODS

9.1 STUDY DESIGN

This is a post approval, multinational, multicenter, observational, prospective cohort study for patients with type 1 diabetes who agree to participate. All patients on Insuman Implantable 400 IU/mL in the MIP will be encouraged to participate in this registry for the duration of the study, which is 10 years from inclusion of the first patient.

This registry will include a cohort of adults with type 1 diabetes some of whom are those already treated with CIPII and included in HUBIN_L_05335 as well as patients with type 1 diabetes placed on implantable pump more recently. Both types of patients in this cohort will be treated under normal conditions of use. This registry plans to collect safety information on the status of each patient with type 1 diabetes treated with Insuman Implantable 400 IU/mL in a Medtronic MiniMed Implantable pump. The information collected will include disease characteristics including comorbidities, concomitant medications and late diabetes complications, some important safety risks (identified and potential), and missing information described in the RMP.

The design of the study will mirror real life clinical practice and management of these patients. The visits will be done according to routine clinical practice for intra-peritoneal insulin (i.e. study entry, ad hoc, and refill visits). Sites will record data for study endpoint assessments at each visit every 40 to 45 days into the clinical record which is the source document and complete the electronic case report form (e-CRF) at least every six months.

In order to evaluate the real-life conditions of use of Insuman Implantable 400 IU/mL in a Medtronic MiniMed Implantable pump, the choice of a non-interventional design is more appropriate than an experimental design. Moreover the characteristics of interest may not be available or with insufficient accuracy in patient's electronic medical records; therefore a prospective mode of data collection for the purpose of the study objectives has been proposed.

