9.6.1 Data collection schedule

The visits will be done according to routine clinical practice for CIPII, which includes routine visits approximately every 40 to 45 days and ad hoc visits for device interventions or BG control. The participating investigator will be asked to record all new patient data including patients new to the study but who may already be on CIPII at entry into the registry. After this initial data entry, sites will collect safety clinical data (AE/SAE) after each contact with the patient (routine scheduled visits every 40 to 45 days or at ad hoc visits). At three and six months after study entry, then every six months (corresponding approximately to the period for four refill visits), other patient data will be recorded in the e-CRF. AE/SAE will have expedited reporting. No post study follow up is required.

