9.6.2.3 Patient data

Data collection at the study entry (i.e. for new patients, the study entry visit should be performed as far as possible at the first clinical visit after pump implantation) will include the following:

- Patients training for pump use assessment,
- Date of signature of the ICF,
- Patient demography: date of birth, sex, weight, and height,
- Insulin history:
 - date of first insulin prescription (duration of type 1 diabetes),
 - indication for IP treatment,
 - initial date of IP treatment,
 - initial date of Insuman Implantable commercial treatment.
- Medical history:
 - Related to the pump use (including occurrence of DKA, hyperglycaemia and severe hypoglycaemia in the year prior to entry into registry or since pump implantation for new patients),
 - Comorbidities:
 - a) hypertension,
 - b) hyperlipidemia,
 - c) cardiovascular diseases.
 - History of diabetes complications (if any):
 - a) active proliferative retinopathy,
 - b) nephropathy,
 - c) neuropathy,
 - d) hypoglycaemic unawareness.
- Concomitant medications will include all medications at this study entry visit.
- Most recent serum glycosylated hemoglobin (HbA1c) value available (and laboratory normal range), with sampling date (No laboratory test is to be drawn in patients for the purpose of the study and timing of test not related to entry into study).
- Most recent urine microalbumin/creatinine ratio available and laboratory normal range, with sampling date (No laboratory test is to be drawn in patients for the purpose of this study).

After each contact with the patients (refill visits -approximately every 40 to 45 days - ad hoc visits or phone calls)

Non-Interventional Post Authorization Safety Study (PASS) Amended Protocol 2 20-Feb-HUBIN-C-06380 - insulin human Version

- Collections of AEs (in expedited manner see safety Section 11), including:
- Severe hypoglycaemia,
- Hyperglycaemia caused by insulin under-delivery (due to pump jamming, pump dysfunction or catheter occlusion),
- Pump pocket infection,
- Abnormal healing,
- Skin erosion,
- Hypersensitivity reaction to Insuman or pump material,
- Focal hepatic steatosis,
- Other AEs, including diabetic complications,
- Pregnancy/lactation.

All AEs will be followed until recovery or stabilization or until the end of the follow-up period, whichever comes first.

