9.7 DATA ANALYSIS

IQVIA will be accountable for the statistical analysis of the study data.

A complete overview of planned analyses and limitations due to sample size reduction will be available in the amended Statistical Analysis Plan (SAP).

Eligible patients will be those who have signed an Inform Consent Form (ICF) and have received at least one dose of Insuman Implantable 400 IU/mL. In this non-comparative cohort study, all data analyses will be purely descriptive and no statistical testing will be performed.

These descriptive analyses will be conducted on the entire study population and specific subpopulations of interest (eg, country).

Summary statistics (mean, standard deviation, median, interquartile range, minimum, and maximum values) will be presented for continuous variables and counts and, if relevant, percentages will be presented for categorical and binary variables.

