9.7.1 Primary analysis

Since the primary objective is to monitor the important identified risks (see Section 9.3.1 for primary endpoints definitions, the analysis will be descriptive and the multiplicity control will not be considered.

- For the important identified risks including severe hypoglycaemia, hyperglycaemia due to underdelivery of insulin, pump pocket infections, skin erosion, and abnormal wound healing, the time to first event will be depicted by the Kaplan-Meier methodology. Globally, the total number assessed will be given and the number and percentage of events/censored will be calculated. For each time point (six-month and each year time-points), the number of patients at risk, the number of events and the probability (Kaplan Meier estimates) of an event and its 95% confidence interval (CI) will be given.
- Graphically, the cumulative risk over the entire study using life table approach, as well as the instantaneous risk expressed as the hazard function over time, will be presented according to the time expressed in years and using a kernel smoothing method.

Moreover, a horizontal line will represent the incidence rate calculated, as number of patients with one or more events divided by the number of patients treated.

- For rare events, the incidence rate using time to event approach will be considered: number of patients with the event, total patients years for the event, and incidence rate per 100 patient-years with its 95% CI will be calculated.

For the analyses purposes, all AEs will be recorded in the study safety database and classified according to Medical Dictionary for Regulatory Activities (MedDRA® version 16.1 or later) by system organ class and preferred terms (PTs).

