8.1.3 Covariates?	\bowtie			26

Non-Interventional Post Authorization Safety Study (PASS) Amended Protocol 2 HUBIN-C-06380 - insulin human

20-Feb-2018 Version number: 1

Section 8: Data sources	Yes	No	N/A	Page Number(s)
8.2 Does the protocol describe the information available from the data source(s) on:				
8.2.1 Exposure? (e.g. date of dispensing, drug quantity, dose, number of days of supply prescription, daily dosage, prescriber)	\boxtimes			26
8.2.2 Endpoints? (e.g. date of occurrence, multiple event, severity measures related to event)	\boxtimes			26
8.2.3 Covariates? (e.g. age, sex, clinical and drug use history, co- morbidity, co-medications, life style, etc.)	\boxtimes			26
8.3 Is a coding system described for:				
8.3.1 Diseases? (e.g. International Classification of Diseases (ICD)-10)			\boxtimes	
8.3.2 Endpoints? (e.g. Medical Dictionary for Regulatory Activities (MedDRA) for adverse events)	\boxtimes			32
8.3.3 Exposure? (e.g. WHO Drug Dictionary, Anatomical Therapeutic Chemical (ATC)Classification System)			\boxtimes	
8.4 Is the linkage method between data sources described? (e.g. based on a unique identifier or other)	\boxtimes			26

Comments:

Sect	ion 9: Study size and power	Yes	No	N/A	Page Number(s)
9.1	Is sample size and/or statistical power calculated?	\bowtie			26

Comments:

20-Feb-2018 Version number: 1

Section 10: Analysis plan	Yes	No	N/A	Page Number(s)
10.1 Does the plan include measurement of excess risks?	\boxtimes			31
10.2 Is the choice of statistical techniques described?	\boxtimes			31
10.3 Are descriptive analyses included?	\boxtimes			31
10.4 Are stratified analyses included?			\square	
10.5 Does the plan describe methods for adjusting for confounding?	\boxtimes			31
10.6 Does the plan describe methods addressing effect modification?			\boxtimes	

Comments:

Section 11: Data management and quality control	Yes	No	N/A	Page Number(s)
11.1 Is information provided on the management of missing data?	\boxtimes			26
11.2 Does the protocol provide information on data storage? (e.g. software and IT environment, database maintenance and anti-fraud protection, archiving)	\boxtimes			26
11.3 Are methods of quality assurance described?	\boxtimes			33
11.4 Does the protocol describe possible quality issues related to the data source(s)?	\boxtimes			33
11.5 Is there a system in place for independent review of study results?	\boxtimes			34

Comments:

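### The pooled time-to-event curves mix long-standing and recent pump users with no stated time origin, and section 9.7 does not carry through the separate analysis offered in section 9.9

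*Protocol*

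**What the plan says.** - **Cohort.** Section 9.1 describes patients already treated and "included in HUBIN_L_05335 as well as patients with type 1 diabetes placed on implantable pump more recently". Section 9.6.1 adds "patients new to the study but who may already be on CIPII at entry into the registry".
- **Primary analysis.** For the five identified risks, section 9.7.1 says "the time to first event will be depicted by the Kaplan-Meier methodology". Estimates are given at six months and at each year, with a kernel-smoothed hazard against time in years. No time origin is given.
- **Start of observation.** Section 11 collects adverse events from signature of the consent form.
- **Acknowledged bias.** Section 9.9 says long-term users, explained in parentheses as those from the clinical trials, may be at lower risk of some events than new users. Its remedy is: "This bias can be addressed by analyzing data separately for long term users and new users".
- **Subgroups.** Section 9.7 extends the descriptive analyses to "specific subpopulations of interest (eg, country" and names no other example. It leaves the complete list to the amended SAP.
- **Checklist (Annex 2).** Item "10.4 Are stratified analyses included" is marked N/A. So are item 5.3 (exposure time windows) and item 5.5 (duration-dependent response).
- **Size.** About 260 patients, based on those already included at Amendment 2. For the future: "No new patient or a very limited number of newly implanted patients is expected".
- **Dates collected at entry.** Section 9.6.2.3 lists the initial date of IP treatment and, separately, the "initial date of Insuman Implantable commercial treatment".

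**The concern.** The study exists to describe the frequency of these risks in practice, long-term safety above all. A reader will take year 1 of a Kaplan-Meier curve for an implanted treatment as the first year on that treatment. In a cohort of this kind it is not: it averages first years with third, sixth or later years. If risk changes with duration, the cumulative risk and the shape of the hazard both depend on the mix of durations at entry, which the protocol does not describe.

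The problem is sharpest for abnormal healing, defined in section 8.1 as occurring at the incision after implantation. A patient implanted long before consent stays in the denominator although that period has largely passed.

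The protocol recognises the bias and offers a remedy. Its own analysis section and checklist then point elsewhere, and the groups needed for the remedy are not workably defined.

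**Working it through.** The plan has no precision figure to reproduce. It states that no formal sample size calculation is made, and 260 is an enrolment count.

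**1. The clock.** Section 9.7.1 fixes time points but no origin. Events count from consent (section 11), and data collection is scheduled from study entry (section 9.6.1). Study entry is therefore the likely origin, by inference. A patient who began IP treatment *a* years before entry is then at *a + t* years on treatment when the curve shows *t*.

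**2. The remedy, side by side.**

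| Place | Content |
|---|---|
| 9.9 | Separate analysis of long-term and new users offered; long-term means from the trials |
| 9.7 to 9.7.3 | Country is the only subpopulation named; no split by duration |
| Checklist 5.3, 5.5, 10.4 | Time windows, duration response and stratified analysis all N/A |
| 9.6.1 | Patients may already be on IP insulin at entry, whether or not they were in a trial |

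Patients implanted outside the trials before entry fit neither label clearly.

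**3. How many new users?** Not stated. A rough ceiling comes from the initial plan of up to 50 new patients per year (section 9.9). From first patient in (April 2016) to Amendment 2 (20 February 2018) is 1 + 10/12 + 20/365 = 1.89 years. Then 50 × 1.89 ≈ 94, and 94/260 = 36%. The number could lie anywhere from a handful to about 94.

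**4. Illustration of mixing.** Assume a hazard of 0.15 per year in the first year after implantation and 0.05 later. Assume also that new users enter at implantation and all others are past year 1. With a share *s* of new users, the pooled one-year risk is

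*s*(1 − e^−0.15) + (1 − *s*)(1 − e^−0.05) = 0.1393*s* + 0.0488(1 − *s*).

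| *s* | Pooled year-1 risk | First-year risk after implantation |
|---|---|---|
| 5% | 5.3% | 13.9% |
| 10% | 5.8% | 13.9% |
| 20% | 6.7% | 13.9% |
| 36% | 8.1% | 13.9% |

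**5. Precision of a new-user stratum.** Exact (Clopper-Pearson) 95% intervals at about 10% observed risk, for assumed sizes:

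- 1/10: 0.3% to 44.5%
- 3/26: 2.4% to 30.2%
- 5/52: 3.2% to 21.0%
- 9/93: 4.5% to 17.6%
- whole cohort, 26/260: 6.6% to 14.3%

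**The case against.** The best defence is that the study is purely descriptive, the bias is disclosed, and section 9.7 leaves the complete list of analyses to an amended SAP that is not at hand. The subgroup list is open, since country is only an example. Risk from entry among current users is a legitimate quantity for monitoring use in practice, and rates per 100 patient-years are already planned for rare events. Much of this stands, and it rules out several stronger readings that a reader might draw:

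- *The split is missing from the SAP.* This cannot be asserted. Only protocol section 9.7 can be said not to carry it.
- *The protocol sets a study-entry clock.* It sets none; study entry is inferred.
- *Most patients enter years after implantation.* No section says so. Section 9.6.2.3 asks that new patients enter, as far as possible, at the first visit after implantation.
- *The new-user group is nearly empty after Amendment 2.* The sentence on new patients concerns future implants, not recent implants already among the 260. The group will hardly grow, but its size is unknown.
- *Only the commercial start date is recorded.* The initial date of IP treatment is recorded too.
- *Early risk is understated by a known amount.* Section 9.9 says only that long-term users may be at lower risk of some events. Section 9.3.1.2 links pocket infection also to refill punctures and catheter replacement, which continue during use. Replacement pumps bring further surgery.
- *The primary time scale must become time since implantation with delayed entry.* Section 9.6.2.3 lists no date of current implantation. Its entry history names ketoacidosis, hyperglycaemia and severe hypoglycaemia, but not infection, healing or erosion.

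Deferral to the SAP does not remove the conflict inside the protocol. Section 9.9 relies on a stratified analysis by duration, and the checklist declares such analyses not applicable.

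**Conclusion.** The point holds as an undefined time origin combined with an internal contradiction. On the likely reading, the pooled curves show risk from study entry in a mix of current users, not risk by time on treatment. The remedy in section 9.9 is not carried into protocol section 9.7, conflicts with checklist items 5.3, 5.5 and 10.4, and rests on a definition by trial membership that leaves some patients unclassified.

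The size is unknown. The 13.9% against 5.3% to 8.1% above depends on assumed hazards and an assumed share of new users. It shows that mixing could matter across the plausible range, not that it does. If the hazard is flat over time, there is no such distortion. The checklist marks are read from an extracted table. The curves remain usable if they are labelled for what they measure.

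**What to change.** 1. State the time origin in section 9.7.1. If it is study entry, describe the pooled curve as risk from study entry in current users.
2. Define long-term and new users by time since initial IP treatment at entry, not by trial membership. That date is already collected. It measures time on the IP route, which may include an earlier insulin product (section 7.1), and the report should say so.
3. Carry the split into section 9.7. Report first-event rates per 100 patient-years with 95% CI by time since IP start (for example <1, 1 to <3, 3 to <7 and ≥7 years), with numbers at risk. State that the first event means the first after study entry.
4. State the number of new users among the roughly 260.
5. Reconcile checklist items 5.3, 5.5 and 10.4 with section 9.9.
6. Optionally, add a delayed-entry curve on time since IP start as supportive. Use time since implantation for the surgical risks only if the implantation date can be obtained from the records.

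The cost is a wording change and modest extra programming. The downside is wide intervals in the shortest-duration bands, which the numbers at risk will make visible.
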